### 3.2 Benefit/Risk assessment

More detailed information about the known and expected benefits and risks and reasonably expected adverse events (AEs) of RESP301 may be found in the Investigator's Brochure.

### 3.2.1 Risk assessment

10 of 10

[REDACTED]

The figure consists of a 3x3 grid of bar charts. The columns represent time periods: 1990 (left), 1995 (middle), and 2000 (right). The rows represent different data series or categories. Each bar is black. In the 1990 column, there are 3 bars in the first row, 1 bar in the second row, and 2 bars in the third row. In the 1995 column, there are 2 bars in the first row, 4 bars in the second row, and 3 bars in the third row. In the 2000 column, there are 1 bar in the first row, 5 bars in the second row, and 4 bars in the third row.

The figure consists of a 5x3 grid of horizontal bar charts. Each chart has a light gray background and black bars. The charts are separated by thin vertical lines. The first chart in the first row has a small black bar at the top. The second chart in the first row has a small black bar at the top. The third chart in the first row has a small black bar at the top. The first chart in the second row has a small black bar at the top. The second chart in the second row has a small black bar at the top. The third chart in the second row has a small black bar at the top. The first chart in the third row has a small black bar at the top. The second chart in the third row has a small black bar at the top. The third chart in the third row has a small black bar at the top. The first chart in the fourth row has a small black bar at the top. The second chart in the fourth row has a small black bar at the top. The third chart in the fourth row has a small black bar at the top. The first chart in the fifth row has a small black bar at the top. The second chart in the fifth row has a small black bar at the top. The third chart in the fifth row has a small black bar at the top.

Potential Risk of Clinical Significance	Summary of Data/Rationale for Risk	Mitigation Strategy
	patient may increase risk of spread of disease	minimise the risk of spread of disease.

### 3.2.2 Benefit assessment

Patients with an underlying respiratory illness (e.g. COPD, bronchiectasis) are at higher risk of adverse outcomes due to exacerbations caused by SARS-CoV-2 or other respiratory infections. To date, no treatment of COVID-19 has demonstrated clinical efficacy. Patients and their physicians are critically in need of treatments that decrease the risk of severe levels of disease, particularly the rate of intubation or other ventilatory support as they significantly lead to fatal outcomes. Considering the current pandemic, even a limited improvement in the rate of progression to severe stage of the disease would provide sizable benefits for patients and society.

[REDACTED]

[REDACTED]

[REDACTED]

[figure not shown]
[REDACTED]

[figure not shown]
[figure not shown]
### 3.2.3 Overall Benefit: Risk Conclusion

Taking into account the measures taken to minimise risk to participants in this study, the potential risks identified in association with RESP301 are justified by the anticipated benefits that may be afforded to participants at high risk of adverse outcomes due to exacerbations caused by SARS-CoV-2 or other respiratory infections.

## 4 Objectives and endpoints

**Table 4-1 Objectives and Endpoints**

Objectives	Endpoints
Primary	

 
• To determine the maximum tolerable dose (MTD) and recommended therapeutic dose (RTD) of RESP301 in patients with mild to moderate COPD or bronchiectasis
 
• To assess the feasibility of recruiting and retaining patients with COPD or bronchiectasis who have viral infection symptoms and treating these patients with RESP301 in a community setting.
 
	
 
• Proportion of patients tolerating RESP301 at each dose level in Part 1 (according to pre-defined criteria)
 
• Feasibility of self-administering RESP301 treatment with nebuliser
 
 
Secondary	
The following secondary objectives will be considered for the cohort as a whole, and in addition for a sub-cohort of those who have confirmed SARS-CoV-2 infection:
 
 
1) To assess the safety and tolerability of RESP301 in patients with COPD or bronchiectasis, who are at high risk of SARS-CoV-2 and other acute respiratory pathogens.
 
 
To be evaluated on the full cohort, and separately in the sub-cohort of those who test positive for SARS-CoV-2:
 
 
1) Safety and tolerability of RESP301
 
 

Objectives	Endpoints
	

2) To collect preliminary data on the efficacy of RESP301 in treating exacerbations in patients with COPD or bronchiectasis.
	
 
• Total counts and cumulative incidence of: 
 
• Adverse Events (AEs)
 
• Serious Adverse Events (SAEs)
 
• Suspected Unexpected Serious Adverse Reaction (SUSARs)
 
• Severe AEs
 
• Treatment-related AEs/SAEs
 
 
 
 
Feasibility in terms of percentage of patients who, having experienced and correctly reported an exacerbation, receive the treatment within [REDACTED] of reporting their exacerbation
 
2) Efficacy of RESP301 [REDACTED]
 

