	
the patient is willing to continue in the study, they will have a rapid delivery of a study pack containing study IMP and nebuliser and other equipment for the trial.
 
Note that if COVID-19 is suspected, the patient will be advised to follow the prevailing NHS guidance on testing for COVID-19 taking into account any specific recommendations for patients with COPD or bronchiectasis. Where serial SARS-CoV-2 swabs are undertaken, data will be collected for analysis.
 
During the treatment period, lasting 7 days, at home/ community setting, patients will be asked to:
 

• Administer RESP301 three times daily at the RTD

• Take daily temperature measurements

• Complete a daily diary to record treatment doses

• Attend a daily call with study coordinator to check compliance, assist with issues with product, and report any AEs and changes to medications or medical history, including COVID-19 test results, if available

 
Each participant will receive a maximum of one course of treatment of RESP301 during the study. Remote follow up visit will be carried out approximately 14 and 28 days following end of treatment to record any AEs and changes to medications or medical history, including COVID-19 test results, if available. Additionally, participants whose symptoms had not returned to baseline by the end of treatment period, will be followed up with a phone call 2 weeks post end of treatment.

Endpoints	
Primary endpoint:
 

• Proportion of patients tolerating RESP301 at each dose level in Part 1 (according to pre-defined criteria)

• Feasibility of self-administering RESP301 treatment with nebuliser in terms of:

○ percentage of patients who, having experienced and correctly reported an exacerbation, commence self-administration of the treatment on the day the treatment is delivered

○ compliance with RESP301 administration schedule over the treatment period: for those participants commencing treatment, the percentage of total doses taken

 
Secondary endpoints:

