# **3. EFFICACY AND SAFETY VARIABLES**

## **3.1 Efficacy**

The primary objective in part 1 (Dose Finding Phase) is to determine the maximum tolerable dose (MTD) and the recommended therapeutic dose (RTD) of the single agent RESP301. For these decisions individual and cohort stopping criteria were defined, see section 7.7.2 and 7.7.3 of the protocol. In a Safety Advisory Committee (SAC) meeting prior to part 2 of this study these doses will be determined. Hence no single primary and/or secondary endpoint for part 1 was defined.

In part 2 (Expansion Phase), the primary endpoints are:

- Percentage of patients entering the dormant period who, having experienced and correctly reported an exacerbation, commence self-administration of the treatment at home on the day the treatment is delivered.
- Percentage of patients who, having experienced and correctly reported an exacerbation, receive the treatment within 48 hours of reporting their exacerbation.
- Compliance with RESP301 administration schedule over the treatment period: for those participants commencing treatment, the percentage of total doses taken.

The secondary endpoints, which will be analyzed by treatment dose and separately in the sub-group of patients who had a positive test result for SARS-CoV-2 are defined as:

- % of participants able to tolerate the test dose in Part 1(a), Part 1(b) and Part 2, i.e. able to complete the test dose without any of the following:
  - o Troublesome cough, chest pain or tightness, bronchospasm or dyspnea that is deemed unacceptable by the patient.
  - o methemoglobin >5% during or >3% post dose (30 or 60 mins)
  - o any treatment-related AE that led to participant not being able to complete the test dose, and/or be suitable to be enrolled into the dormant period in the Investigator's opinion
  - o for the first 50 patients who will undergo pre and post-test dose spirometry, >20% reduction in FEV1 from pre-test dose to post

---

test at 60 min dose with symptoms listed above (patients with >20% reduction in FEV1 without symptoms would be offered the option to continue in the study).

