## **5. METHODS OF ANALYSIS AND PRESENTATION**

### **5.1 General Principles**

The statistical analysis will be performed using the validated software package SAS version 9.4 or higher (SAS Institute Inc., Cary, NC 27513, USA).

All recorded and derived variables will be presented by treatment group and visits (if appropriate) using descriptive summary tables (continuous data: sample size, mean, standard deviation (SD), minimum, median, maximum; categorical data: sample size, absolute and relative frequency).

The mean and median will be presented to one more decimal place than the raw data. The SD will be presented to two more decimal places than the raw data. The percentages will be presented to 1 decimal place. In all the summaries, the treatment groups will be displayed in the following order: part 1 (RESP301 1 ml, 2 ml, ...6 ml, RESP+Vent 6 ml) and then part 2.

For all parameters, baseline is defined as the last available pre-treatment value (i.e. the last non-missing value available before study drug administration. In general, missing data will be treated as missing and no attempts will be made to impute values for missing data.

No formal interim efficacy analyses are planned in this study; however, several safety interim analyses by the Safety Advisory Committee (SAC) will be performed as detailed in the protocol, see section 7.7 for part 1 and an Independent Data Monitoring Committee (IDMC) will review the safety data on an ongoing basis as described in the DMC charter, see section 10.6 of the protocol.

Subjects who did not receive any study medication (screening failures) will be listed separately and not presented in any table or figure, except in the patient's disposition table.

The versions of the following international dictionaries (MedDRA version 26.1 and WHO DD, version 2024) will be used for medical coding:

Adverse events: Medical Dictionary for Regulatory Activities (MedDRA).

Medical Histories: Medical Dictionary for Regulatory Activities (MedDRA).

Medications: World Health Organization (WHO) Drug Dictionary including Anatomical Therapeutic and Chemical (ATC) classification.

If a medication in the drug dictionary (DD) table is associated with more than one ATC code, the first ATC code will be assigned to that medication.

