### **5.3 Disposition of Subjects**

A summary of the subject disposition will be created including number of patients screened, number of screen failures, if any, number of patients treated, number of patients who completed the study in each treatment group. In addition, a summary of the number and percentage of patients in the safety set who were available at each visit will be presented by treatment group and overall.

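### Recruiting and retaining patients is a primary objective with no endpoint, and the SAP's withdrawal and visit outputs would leave out dormant participants who never inhale drug

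*Protocol*

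**What the plan says.** **Objective.** Protocol Table 4-1 lists among the primary objectives "To assess the feasibility of recruiting and retaining patients with COPD or bronchiectasis who have viral infection symptoms", together with treating them in the community. The synopsis repeats this under Objectives and under Statistical planning. Protocol 5.1 and SAP 2.1 give it as the purpose of Part 2.

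**Endpoints.** Table 4-1 pairs the objective with "Feasibility of self-administering RESP301 treatment with nebuliser". Detail in that table is redacted, but the synopsis gives the two components in full:
- "percentage of patients who, having experienced and correctly reported an exacerbation, commence self-administration of the treatment on the day the treatment is delivered"
- compliance, defined as "for those participants commencing treatment, the percentage of total doses taken"

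SAP 3.1, in the list that opens "In part 2 (Expansion Phase), the primary endpoints are", keeps both and adds a third: "Percentage of patients who, having experienced and correctly reported an exacerbation, receive the treatment within 48 hours of reporting their exacerbation". The protocol has that item as secondary. The remaining secondary endpoints cover safety, tolerability and efficacy.

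**Populations.** The SAP 5.2 safety set requires at least one complete or partial inhaled dose. SAP 5.3 plans a summary of the "number and percentage of patients in the safety set who were available at each visit". The study withdrawal table (Table 1.2 of section 15.1) and the end-of-study listing (Appendix 16.2.1, Listing 1) are also on the safety set. SAP 5.1 states: "Subjects who did not receive any study medication (screening failures) will be listed separately and not presented in any table or figure". The same sentence then exempts the disposition table, which is planned on all screened patients (Table 1.1 of section 15.1).

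**Screen failures.** Protocol 6.5 reserves the term for people who consent and then prove ineligible.

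**The concern.** A primary objective should have a stated measure, a denominator and a population, and recruiting and retaining have none of these. Part 2 places at least 150 people in a dormant period of up to 12 months, and the SAP expects 30 of them to exacerbate. The other 120 can inform recruitment and retention but no listed feasibility endpoint, because those endpoints begin only once an exacerbation has been reported.

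The descriptive outputs that might fill the gap use a population defined by inhaling drug. A dormant participant who had no test dose and no exacerbation is enrolled and eligible, and may be followed for a full year, yet lies outside the safety set. Under SAP 5.1 that person also carries a label that protocol 6.5 gives to ineligible people. If the label were applied in the disposition table, a retained participant would be reported as a screen failure, which would distort both the recruitment and the retention counts.

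**Working it through.** **1. Match the objective to the endpoints.** The denominators are:

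| Endpoint | Denominator | Recruitment? | Dormant retention? |
|---|---|---|---|
| Treatment started on delivery day | those who reported an exacerbation | no | no |
| Treatment received within 48 hours | those who reported an exacerbation | no | no |
| Percentage of doses taken | those who started treatment | no | no |

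The secondary safety, tolerability and efficacy endpoints measure neither. Redaction does not account for this, since the synopsis and SAP lists are readable.

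**2. Reproduce the plan's own figures.** Part 2: 50 test-dosed + 100 further = 150, which agrees. Expected exacerbations (SAP 4): 30/150 = 20%. The documents give no derivation of the 30, and no dropout rate.

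**3. Count those outside the safety set if the DMC waives the test dose.** Assume that each untested participant who exacerbates inhales at least one dose, and that the same exacerbation proportion p applies to tested and untested participants.

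Never dosed = (100 − R) × (1 − p), where R is the number of already-dosed Part 1 participants among the untested 100.

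- SAP figure, no rollover: 100 × (1 − 0.20) = **80**. The Part 2 safety set is then 50 + 100 × 0.20 = 70 of 150.
- Higher exacerbation rate: protocol 3.1 cites 0.85 per person for moderate COPD. Assuming this is annual and Poisson, p = 1 − exp(−0.85) = 0.573, giving 100 × 0.427 = **about 43**.
- SAP figure, full rollover: Part 1 has up to 7 × 8 = 56 participants. If all 56 enter Part 2 within the untested 100, (100 − 56) × 0.80 = **about 35**.
- The DMC keeps the test dose: everyone inhales drug, so **0** are omitted for this reason.

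**4. Compare the outputs that could show retention.**

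| Output | Population | Untested, never-exacerbating dormant participants |
|---|---|---|
| By-visit availability (SAP 5.3) | safety set | left out |
| Study withdrawal (Table 1.2, section 15.1) | safety set | left out |
| End-of-study listing (Appendix 16.2.1) | safety set | left out |
| Disposition (Table 1.1, section 15.1) | all screened | included, possibly as screen failures |
| Flow diagram (protocol 10.4.1) | assessed and enrolled | included |

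The disposition content in SAP 5.3 is patients screened, screen failures, treated and completed. It has no line for entry to the dormant period or withdrawal during it.

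**The case against.** The strongest reply is that the information is not lost. Protocol 10.4.1 plans a flow diagram with the number assessed, reasons for exclusion, the number enrolled, and early withdrawals with their primary reasons. It is not limited to dosed participants, and nothing in the SAP withdraws it. The disposition table covers all screened patients and is expressly exempt from the SAP 5.1 exclusion. A screened-to-enrolled ratio and an overall withdrawal proportion could be taken from these outputs. This stands, and it rules out the inference that the objective cannot be answered. What is missing is a named measure, its denominator and the right population for the detailed tables.

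Second, the screening-failure parenthesis in SAP 5.1 may be loose wording, and protocol 6.5 has the correct definition. That is fair: miscounting is a risk, not a certainty. The two texts still conflict, and the safety-set restriction on the three outputs does not depend on the label.

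Third, the objective speaks of patients with viral infection symptoms, so it could be read as covering only those who exacerbate, all of whom are in the safety set once dosed. The scope is arguable. However, protocol 5.1 refers to recruiting and retaining patients with pre-existing respiratory disease at higher risk. Neither reading supplies a recruitment measure.

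A reader might also infer that safety-set retention must be biased upward, because untested participants enter that set only if they are still in contact when they exacerbate. The documents do not establish this. The safety set also holds people who took the test dose and did not go on to the dormant period (SAP Table 3, footnote 1), and their absence at later visits pulls availability down. The net direction is unknown.

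**Conclusion.** The point holds in a limited form. Recruitment and retention form a primary objective that no primary or secondary endpoint measures, whatever the DMC decides. The withdrawal table, by-visit summary and end-of-study listing use the wrong population for retention in Part 2, and the SAP 5.1 label contradicts protocol 6.5.

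The number left out ranges from 0 to about 80 of the 100 untested participants. The upper figure needs three things together: the DMC waives the test dose, 20% exacerbate (the protocol calls 30 a minimum), and few Part 1 participants roll over. A reader might conclude that more than half of Part 2 drops out of these outputs (80/150 = 53%), but that share holds only when all three conditions are met. Overall counts would still be available from the disposition table and the flow diagram.

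**What to change.** 1. For Part 2, run Table 1.2 of SAP section 15.1, the by-visit availability summary in SAP 5.3 and the end-of-study listing on all dormant-period entrants, dosed or not.
2. In SAP 5.1, restrict screening failures to the protocol 6.5 definition. In SAP 5.3, add dormant-period entrants and dormant-period withdrawals to the disposition table.
3. In protocol Table 4-1 and SAP 3.1, add two descriptive feasibility endpoints: the screened-to-enrolled proportion, and the percentage of all dormant entrants still in the study at first exacerbation or Week 52, with an exact 95% confidence interval.

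The cost is wording in both documents and one or two extra descriptive tables. The screening and enrolment log, monthly calls and early-withdrawal assessments are already planned, so no new procedure is needed, provided that the outcome of each monthly call is recorded.

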## 5 Study design

### 5.1 Overall design

This is an open-label, single arm, multicentre study to investigate the feasibility, safety and tolerability of RESP301 in patients with pre-existing respiratory disease who are at higher risk of adverse outcomes such as hospitalisation and/or death due to exacerbations caused by SARS-CoV-2 or other respiratory infections. The study is conducted in a clinical setting in Part 1 [REDACTED] Part 2 of the study will assess the feasibility of recruiting and retaining these patients in a community setting [REDACTED]  
[REDACTED]  
[REDACTED]

#### Part 1(a): Dose Finding Phase

In Part 1(a), [REDACTED] subjects with COPD will be enrolled in separate cohorts to receive a single dose of [REDACTED] or [REDACTED] of RESP301. Each cohort will comprise [REDACTED] subjects. This part of the study will consist of one visit in which subjects receive a single dose of RESP301 in the clinic on Day 1, with a follow up safety phone call being conducted on the morning of Day 2 to check for any adverse events. Enrollment to these cohorts will be sequential and subsequent cohorts will only be enrolled after safety review of the previous cohort. The safety reviews will be conducted by the safety advisory committee (SAC), comprising the site Principal Investigators (or delegates) and the Sponsor's Executive Medical Officer as a minimum.

[REDACTED]

○ [REDACTED]  
■ [REDACTED]  
■ [REDACTED]  
■ [REDACTED]  
■ [REDACTED]  
■ [REDACTED]

[REDACTED]  
[REDACTED]  
[REDACTED]  
[REDACTED]

Subjects can receive more than one dose level as long as they did not meet individual stopping criteria from any given prior dose.

### **Part 1(b): Concomitant Medication Expansion Phase**

In part 1(b) up to [redacted] patients with COPD or bronchiectasis will be enrolled into a cohort to receive a short-acting inhaled bronchodilator (2 inhalations of Ventolin - [redacted] per inhalation) through a spacer device 10 minutes before receiving a single dose of RESP301 at the MTD determined in part 1(a). Subjects will continue Standard of Care medication prior to receiving RESP301 apart from their usual short acting bronchodilators which will be withheld for [redacted] before dosing with RESP301. Pre-dose short acting bronchodilator will then be administered in clinic.

Subjects from Part 1a may also enter Part 1b (if deemed eligible).

This part of the study will operate under the same oversight, monitoring and follow up criteria as Part 1(a)

### **Part 2: Expansion Phase**

#### **Baseline Visit**

Once the RTD has been established in Part 1, [redacted]

- [redacted]
- [redacted]

During the visit participants who satisfactorily tolerate the test dose will be enrolled into the “dormant period”.

All patients including those receiving the test dose will undergo the following procedures

- Informed consent
- Inclusion and exclusion criteria
- Any medical assessments (e.g. heart or lung examination) which in the PI's opinion are required to assess whether the patient is suitable for the trial
- Demographic information
- Medical history and concurrent medications
- Height and weight
- Vital signs
- Pulmonary function tests (FEV1, FVC and % predicted), if required

Subjects that participate in Part 1 and do not meet any of the individual stopping criteria can enrol in Part 2. Eligibility criteria will be reassessed prior to entering Part 2 of the trial. Participants who have not satisfied inclusion/exclusion criteria will be excluded from continuing in the study.

An independent Data Monitoring Committee will review the data from the [REDACTED] participants that received RTD. Based on the data from these participants, it will be decided whether test doses should be administered to further participants for the remaining duration of the study.

